3.1.2 Study Interventional Phase

The study interventional phase will occur during the intraoperative period from after placement of second IV line or bolus of propofol (if IV line is present prior to induction) to the last stimulus.

EEG Monitoring

EEG monitoring will start after induction and end after the last stimulus.

Stimuli

At steady-state EEG SEF, two research stimuli (placement of oral pacifier and electrical stimulation) will be performed by the study investigator(s). The third stimulus, laryngoscopy—a clinically required procedure, will be performed by the anesthesia team on record caring for the patient.

Propofol dosing

Adjustment to propofol infusion and dosing is considered standard of care and is needed to achieve different anesthetic depths and SEF targets for different stimuli. As described in the study flowchart below, if current SEF is below target SEF, then propofol dose will be decreased. Conversely, if current SEF is above target SEF, then propofol dose will be increased.

Second IV Placement

An IV separate from the propofol infusion line will be placed in order to draw blood samples to evaluate propofol plasma concentration. Often the second IV will also be clinically indicated regardless of study status. If the second IV line is unable to be placed, a butterfly needle may be used to draw a single sample.

Blood Sample Collection

Up to three 1ml blood samples, for a total of 3ml, will be collected during the study interventional phase.

3.2 Study Duration, Enrollment and Number of Sites

3.2.1 Duration of Patient Study Participation

The study duration for each patient will be the day of the procedure during the intraoperative period.

3.2.2 Total Number of Study Sites/Total Number of Patients Projected

The study will only be conducted at CHOP. It is expected that approximately 150 patients will be enrolled to produce 120 evaluable patients, 60 each in the 3-12mo and 13-24mo age groups.

3.3 Study Population

3.3.1 Inclusion Criteria

- 1) Children 3 to 24 month old undergoing a procedure.

- 2) Planned laryngoscopy and endotracheal intubation or laryngeal mask airway (LMA) placement for clinical care.
- 3) Planned propofol anesthesia for anesthesia maintenance during study period.
- 4) ASA < III.
- 5) Muscle relaxant not indicated per planned clinical care for laryngoscopy/intubation or LMA.
- 6) Anticipated procedure duration approximately < 2h40min

3.3.2 Exclusion Criteria

- 1) Patients undergoing an emergency procedure.
- 2) Known severe neurological disease which might result in abnormal EEG SEF.
- 3) Deformities of forehead (difficult EEG sensor placement).
- 4) Known difficult airway.
- 5) Allergy to propofol.
- 6) Attending anesthesiologist on record caring for patient plans to administer additional IV medication besides propofol during study phase.
- 7) Currently on anti-seizure medication (might alter propofol pharmacodynamics).

Patients that do not meet all of the enrollment criteria may not be enrolled. Any violations of these criteria must be reported in accordance with IRB Policies and Procedures.

4 STUDY PROCEDURES

4.1 Screening Phase

Procedures below will be performed during the screening phase.

- Informed Consent/HIPAA authorization
- Medical Record Review

4.2 Study Interventional Phase

4.2.1 EEG Recording

[figure not shown]
After anesthesia induction, Masimo Sedline EEG will be applied to the patient's forehead and recording will continue until after the last stimulus.

4.2.2 Stimuli

Two research stimuli: placement of oral pacifier and electrical stimulation will be performed by the study investigator. The third stimulus, laryngoscopy, will be performed by the anesthesia team on record caring for the patient. The stimulus will be performed after the patient has achieved steady state at target EEG SEF, as described in the flowchart below. The response to each of the three stimuli (Yes/No) will be recorded. Given time constraints, not all three stimuli may be performed on each patient. Each research stimulus may only be

applied once to each patient. The flowchart below shows the study procedures. Details of the stimuli are below:

- 1) Placement of oral pacifier involves placing a soft pacifier inside the patient's mouth.
- 2) Electrical stimulation is typically done to assess neuromuscular function.
- 3) Laryngoscopy is done prior to intubation (placement of breathing tube) and is considered a clinically-required procedure for all patients.

4.3 Patient Completion/Withdrawal

Parents or caregivers may withdraw the patient from the study at any time without prejudice to their care. They may also be discontinued from the study at the discretion of the responsible attending anesthesiologist on record and/or study investigator due to unforeseen circumstances (unable to establish IV access, lack of time, unable to achieve steady state SEF, etc...). The placement of the second IV will occur alongside routine clinical care. It will not result in additional anesthesia time as standard care is able to continue while the IV is being placed. If the study investigator becomes aware of any serious, related adverse events after the patient completes or withdraws from the study, they will be recorded in the source documents and on the CRF.

5 STUDY EVALUATIONS AND MEASUREMENTS

5.1 Screening and Monitoring Evaluations and Measurements

5.1.1 Medical Record Review

- PHI: MRN, name, element of dates including birth date and service dates
- Demographic
- Anesthetic records
- Medication list
- Surgical records
- Post operative recovery records
- Expected procedure duration and procedure type
- ASA status

5.1.2 EEG Monitoring

The study team will assess skin integrity prior to applying the EEG sensor. After anesthesia induction, the Masimo EEG sensor will be placed on the forehead and connected to the EEG monitor. EEG monitoring for the study will continue until laryngoscopy. The Masimo EEG monitor will automatically calculate and display EEG SEF values.

5.1.3 Propofol Dosing

Propofol will be administered via an infusion pump with initial dosing based on a published dosing table used in CHOP clinical practice (table 1).¹² This table serves as a starting guide to dosing, ultimately EEG SEF will be used to titrate propofol dose. Propofol dosing adjustments to achieve target SEF are described in section 5.1.8 below.

Table 1
Dosing regimens for propofol in neonates, infants, and children

Age Group	0–1 mo	1–3 mo	3–6 mo	6–12 mo	12–36 mo	3–12 y
Propofol bolus mg/kg	3.5	3	3	3	3	2.5
Propofol 0–15 min (µg/kg/min)	183	200	200	208	217	250
Propofol 16–30 min (µg/kg/min)	167	183	192	200	200	217
Propofol 31–60 min (µg/kg/min)	150	167	175	183	192	183
Propofol 61–120 min (µg/kg/min)	133	158	167	175	183	167
Propofol 121–180 min (µg/kg/min)	117	150	158	167	175	150
Propofol 181–300 min (µg/kg/min)	100	133	150	158	167	142

5.1.4 Stimuli

For this study, laryngoscopy is clinically required for anesthesia and the procedure, whereas electrical stimulation are often performed, but may not always be clinically required.

Depending on time constraints, each patient may have two to three stimuli applied in sequence (placement of oral pacifier, electrical stimulus, and laryngoscopy). Based on responses to each stimulus, the SEF target and propofol dose may be adjusted for the next

stimulus. Each stimulus may only be applied once per patient and all stimuli will be completed prior to intubation.

If sevoflurane was used during anesthesia induction, then sevoflurane will need to be washed out prior to performing the first stimuli, to avoid residual sevoflurane's effects on the brain and EEG. This can be done by turning off sevoflurane to allow the patient to expire the sevoflurane through breathing. Sevoflurane washout is complete when end tidal sevoflurane concentration < 0.2%. Propofol infusion and EEG monitoring will start prior to completing sevoflurane washout.

Placement of oral pacifier

After anesthesia induction, sevoflurane washout (if applicable), and EEG SEF at the target for placement of oral pacifier, an oral pacifier will be placed in the patient's mouth. The oral pacifier will be withdrawn if there is a positive response (defined in section 5.1.5) or when 5 seconds has elapsed.

Electrical stimulus

The study team will assess forearm skin integrity prior to applying the nerve stimulator electrodes. After sevoflurane washout (if applicable) and EEG SEF at the target for electrical stimulus, a nerve stimulator (Halyard EZstim, Halyard Health Inc) will be initiated at 50hz 30mA for up to 15 seconds.³⁰ The electrical stimulus will stop if there is a positive response (defined below) or when 15 seconds has elapsed.

Laryngoscopy

After sevoflurane washout (if applicable) and EEG SEF at the target for laryngoscopy, laryngoscopy will be performed by the anesthesia team on record caring for the patient. This will mark the end of the stimuli interventions. If no response to laryngoscopy is elicited, the anesthesia team on record may choose to intubate the patient or administer additional medications. If a positive response to laryngoscopy is elicited, the anesthesia team on record may choose to stop laryngoscopy and/or administer additional medications such as neuromuscular relaxant.

Responses to the stimuli will be recorded. The patient will be monitored closely by the study team for any adverse events. Study interventions will occur simultaneously with routine clinical anesthesia and surgical care; therefore, there will be no additional time under anesthesia from this study. Not every patient will have all three stimuli performed and some patients may have only one research stimuli performed. Study procedures will be stopped once all standard, clinical care preparation for surgery is completed.

The same stimulus will not be applied twice to the same patient. The patient's study involvement will conclude once laryngoscopy has been performed on the patient and blood

draw (if applicable) has been performed. The remainder of the anesthetic will be per routine care.

5.1.5 Responses to Stimuli

A positive response to the stimuli described above is occurrence of any of the following: swallowing, sucking, eye opening, facial movement, gross limb movement towards the source of stimulus, and additionally for laryngoscopy, breathing-holding, closure of vocal cords, and coughing. These responses typically occur at the subconscious level without causing awareness of the stimulus. Patient response (Yes/No) will be recorded for each stimulus applied.

5.1.6 Blood collection

Before a stimulus is applied, the SEF value and vital signs will be recorded and a 1ml blood sample will be obtained (not from the propofol infusion IV line). Up to three blood samples may be collecteds..

5.1.7 Dixon Up-Down Technique

Using *Dixon up-down* technique, the current patient's response to stimulus at a SEF target will determine the next patient's SEF target for the same stimulus, thus forming the sequential design method. Using placement of oral pacifier as an example and SEF step size of 2hz, patient #1 starts at SEF target of 18hz and has a positive response to placement of oral pacifier. Patient #2 will have a decrement of SEF target by one step size to 16hz (18 minus 2) for the same stimulus. If patient #2 also has a positive response to placement of oral pacifier, then patient #3 will have a further decrement in SEF target by one step size to 14hz (16 minus 2). If patient #3 has a negative response to placement of oral pacifier, then patient #4 will increase SEF target one step to 16hz (14 plus 2). This continues until there are consecutive crossovers (typically six up-down-up-down...), whereby the median SEF and standard deviation can be calculated for the specific stimulus.²⁴ Since each stimulus is of varying intensity, it's expected that each of the 3 stimuli will have its own *Dixon up-down* calculated SEF target.

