The study will be performed at CHOP. Up to 150 patients who are undergoing procedures under general anesthesia will be enrolled to produce 120 evaluable patients with 60 in each of two age groups (3-12mo and 13-24mo).

Study Interventions and Measures:

For each patient, up to three stimuli will be done in sequence (placement of oral pacifier, electrical stimulation, and laryngoscopy—a clinically required procedure). Propofol dosing will be adjusted to achieve a target EEG SEF for each stimulus. EEG SEF is used as a biomarker of anesthetic depth. The response to the stimulus and EEG SEF will be recorded, along with obtaining a 1ml blood sample. Obtaining the blood sample may not always coincide with the stimulus and up to three blood samples may be drawn per subject. Between different stimuli on the same patient, adjustments to propofol dosing may be

required to achieve a different SEF target. After each study patient, the response to the stimulus will be used to adjust the EEG SEF target for the next patient.

At the end of the study, the median EEG SEFs (EEG SEF₅₀) for each of the three stimuli will be determined. The propofol Ce that corresponds to each EEG SEF will be determined from a regression curve of SEF vs propofol plasma concentration obtained from 1ml of patient blood and measured in a pharmacodynamics laboratory. The study will only be performed by the investigators listed in the study.

PROTOCOL SYNOPSIS

Study Title	EEG to assess propofol anesthetic depth in infants and toddlers
Funder	Departmental funds

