Sequential allocation trial using *Dixon's* up-down technique. To achieve the EEG SEF target, initial propofol dosing will be based on a published age-based dosing table used clinically at CHOP. The EEG SEF target for a specific stimulus will be determined by the previous patient's response to that same stimulus. If the previous patient responded to the stimulus, then the current patient will have a lower SEF target for the same stimulus. Conversely, if the previous patient did not respond to the stimulus, then the current patient will have a higher SEF target for the same stimulus. In the same patient, propofol dose adjustments may be needed between stimuli to achieve different SEF targets. The patient response to stimulus and EEG SEF will be recorded, along with a 1ml blood sample to determine propofol plasma level at a later date in the pharmacodynamic laboratory. The study will only be performed by the investigators listed in the study.

Patient Population**key criteria for Inclusion and Exclusion:****Inclusion Criteria**

- 1) Children 3 to 24 month old undergoing a procedure
- 2) Planned laryngoscopy and endotracheal intubation or LMA placement for clinical care
- 3) Planned propofol anesthesia for anesthesia maintenance.
- 4) ASA < III.
- 5) Muscle relaxant not indicated per planned clinical care for laryngoscopy/intubation.
- 6) Anticipated procedure duration approximately < 2h40min

Exclusion Criteria

- 1) Patients undergoing an emergency procedure
- 2) Known severe neurological disease which might result in abnormal EEG SEF.
- 3) Deformities of forehead (difficult EEG sensor placement).
- 4) Known difficult airway.
- 5) Allergy to propofol.

	
6) Attending anesthesiologist on record caring for patient plans to administer additional IV medication besides propofol during study phase.
 
7) Currently on anti-seizure medication (might alter propofol pharmacodynamics).

Number Of Patients	Up to 150 enrolled patients to produce 120 evaluable patients.
Study Duration	Each patient's participation will last from start of anesthesia to the last study stimulus.
Study Phases	From placement of second intravenous (IV) line or bolus of propofol (if IV is already present prior to induction) to the end of the last stimulus performed. Eligibility screening via reviewing procedure schedule and obtaining informed consent.
Screening	
Study	

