5.1.8 Achieving SEF target

The EEG SEF targets will be different for each of the three stimuli (e.g., the propofol dose and anesthetic depth to block response to placement of oral pacifier is less than for electrical stimulation and laryngoscopy). Based on our clinical experience, the initial SEF targets for the first patient will be 20, 14, and 10hz for placement of oral pacifier, electrical stimulation, and laryngoscopy, respectively. For the same stimulus, the subsequent patient's target SEF will be determined by the previous patient's response to that stimulus, as

described in the section *Dixon up-down technique*. After sevoflurane washout (if applicable) and the propofol infusion dose and SEF are constant for 5 minutes, to ensure equilibration between propofol brain Ce and plasma concentration, the stimulus will be applied as described in the section *EEG vs Propofol Ce*. If current SEF is higher than target SEF, additional propofol (0.5-2mg/kg boluses and/or 10-20% increases in propofol infusion rate) can be given to decrease SEF closer to target SEF. Conversely, if current SEF is lower than target SEF, propofol infusion rate can be decreased 10-20% or temporarily paused to increase SEF to target SEF.

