6.3.2 EEG SEF

[figure not shown]
The median EEG SEF (SEF_{50}) for a stimulus is the SEF where half the patients do not respond to that particular stimulus. SEF_{50} will be determined for each of the three stimuli for the 3-12 mo and 13-24 mo age groups. For each stimuli, each SEF crossover pair (Yes to No response or vice versa) in the *Dixon's up-down* response will be treated as a SEF pair and the mean SEF_{50} and standard deviation of the SEF pairs will be determined. See figure below for example of Dixon's up-down method and determination of SEF_{50} for laryngoscopy. X axis represents sequential patients #1 to #30, Y axis represent SEF levels. Each blue (Yes response) and red (No response) dot represent a patient. The orange bars on the X axis represent crossover pairs, used to calculate SEF_{50} .

In the laryngoscopy example below, the mean SEF_{50} is 8.22hz and standard deviation is 1.83hz, derived from crossover points: 5, 9, 9, 9, 9, 9, 7, 7, 5, 7, 7, 7, 7, 11, 11, 11, 9, 9hz.

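### The up-down allocation rule carries no age-group condition and a six-crossover end point, while SEF50 is sized and estimated per age group with 30 patients per stimulus

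*Protocol*

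**What the plan says.** **Allocation.** Four places in the protocol state the rule, and none conditions on age group.
- Abstract: "After each study patient, the response to the stimulus will be used to adjust the EEG SEF target for the next patient".
- Synopsis, Study Design: "If the previous patient responded to the stimulus, then the current patient will have a lower SEF target for the same stimulus". The converse follows for a patient who did not respond.
- Section 5.1.7: the current patient's "response to stimulus at a SEF target will determine the next" patient's target for the same stimulus.
- Section 5.1.8 repeats this and gives one set of starting values: "the initial SEF targets for the first patient will be 20, 14, and 10hz" for the three stimuli.

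**Estimation and sizing.** These are by age group. Section 6.3.2 says SEF50 "will be determined for each of the three stimuli for the 3-12 mo and 13-24 mo age groups". Section 6.3.4 proposes 30 per stimulus per age group and gives age-related EEG change as the reason for having two groups. SAP item 1 analyzes each stimulus separately by age group and ends with six values.

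**End of a sequence.** Section 5.1.7: "This continues until there are consecutive crossovers (typically six", after which the median and SD can be calculated. Section 6.3.4 gives 30. In the laryngoscopy example in 6.3.2, "X axis represents sequential patients #1 to #30", and the result is "derived from crossover points: 5, 9, 9, 9, 9, 9, 7, 7, 5, 7, 7, 7, 7, 11, 11, 11, 9, 9hz". The SAP has no stopping rule.

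**Estimator.** The synopsis and 6.3.2 use the mean of crossover pairs. The SAP uses CIR with shrinkage, and ordinary isotonic regression as a sensitivity analysis.

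**The concern.** The rule for setting the next target is what staff apply patient by patient. As written it produces three running target lists, one per stimulus, while the analysis needs six. If thresholds differ by age, which is the protocol's own reason for splitting the groups, a shared list sits between the two groups' SEF50s. Each group is then tested away from its own 50% point.

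The end point has a similar gap. Six crossovers and 30 patients are different sample sizes, and no passage says which governs. Applied as a stop, the crossover rule would end most sequences at about a third of the planned size. At stake is the precision of six SEF50 estimates and, under the protocol's crossover mean, the size of any age difference reported.

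**Working it through.** **1. The plan's own figures.** Section 6.3.4: 30 patients with pacifier plus laryngoscopy and 30 with electrical stimulation plus laryngoscopy make 60 per age group, and 60 × 2 = 120. This reproduces. The 18 crossover points in 6.3.2 sum to 148. The mean is 148/18 = 8.22 Hz. The squares sum to 1,274, so SD = √[(1,274 − 148²/18)/17] = 1.83 Hz. Both reproduce.

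**2. The example as a sequence.** Inputs are the 18 points read as midpoints, the 2 Hz step (5.1.7) and the 10 Hz laryngoscopy start (5.1.8). Targets run 10, 8, 6, 4 (first crossover, midpoint 5, patient 4), then 6, 8, 10 (midpoint 9, patient 7), and so on. Crossovers fall at patients 4, 7, 8, 9, 10, 11, 13, 14, 16, 18, 19, 20, 21, 24, 25, 26, 28 and 29. The sixth is at patient 11, yet the example runs to patient 30. So the protocol's illustration follows the 30 and does not stop at six. Its length also fits one age group, since a shared sequence at the planned size would have 2 × 30 = 60 patients.

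**3. Simulation model.** The chance of a response at target t is Φ((t − μ)/σ), where μ is the group's SEF50. The next target is t − 2 after a response and t + 2 otherwise. The start is 10 Hz, the average SEF50 of the two groups is 9 ± 1 Hz, and the age order is random. The documents give neither σ nor an age difference. I assume σ = 1.83 Hz (range 1.0 to 3.5) and differences of 0 to 4 Hz. The 1.83 is only the SD of the example's crossover points. RMSE = √mean[(estimate − μ)²].

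**4. Shared versus separate sequences, 30 per age group, σ = 1.83.**

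| True age difference (Hz) | 0 | 2 | 4 |
|---|---|---|---|
| CIR RMSE, separate | 0.54 | 0.54 | 0.54 |
| CIR RMSE, shared | 0.59 | 0.64 | 0.74 |
| Difference shown by CIR, shared | 0 | 2.09 | 4.04 |
| Difference shown by crossover mean, separate | 0 | 1.95 | 3.90 |
| Difference shown by crossover mean, shared | 0 | 0.76 | 1.76 |

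The precision loss in equivalent patients is 30 × (RMSE separate / RMSE shared)²:
- at 0 Hz, 30 × (0.54/0.59)² ≈ 25
- at 2 Hz, 30 × (0.54/0.64)² ≈ 21
- at 4 Hz, 30 × (0.54/0.74)² ≈ 16

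At a true 2 Hz, as σ goes from 1.0 to 3.5, the shared crossover mean shows 1.10 down to 0.39 Hz. That estimator pairs successive patients of the same age group whose responses differ. It is my construction, because the documents define no within-age pair for a shared sequence.

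**5. Stopping at six crossovers in total.** Across the three stimuli, with the 5.1.8 starting targets and assumed average SEF50s of 9, 12.5 and 16 Hz, the sixth arrives at median patient 9 to 11 (5th to 95th percentile 7 to 16).

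| Assumed σ (Hz) | CIR RMSE at 30 patients | CIR RMSE at sixth crossover | Ratio |
|---|---|---|---|
| 1.0 | 0.32 | 0.57 | 1.8 |
| 1.83 | 0.54 | 0.85 | 1.6 |
| 3.5 | 0.96 | 1.40 | 1.5 |

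**The case against.** The best defense is that the documents point one way. Section 6.3.4 sizes each stimulus within each age group, the 6.3.2 example has exactly that length, and SAP item 1 plots and analyzes by age group. No passage suggests sharing. The phrase on six crossovers is qualified by *typically* and may only describe when an estimate becomes calculable, in which case six as a minimum and 30 as the plan are compatible. The SAP, revised in April 2024, uses CIR, which is nearly unbiased even with shared sequences.

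Most of this stands. It shows what was probably meant, and it limits the damage. It does not put the condition into the sections that staff follow. Nor does it remove a sentence in the operative section that tells the reader when a sequence ends.

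Three stronger readings are tempting and are not supported:
- *That the sequences were shared.* The documents do not say so, and the sizing and the example suggest otherwise.
- *That the age-specific SEF50s will be biased.* This needs shared sequences, a real age difference and a within-age crossover mean. The SAP's estimator avoids nearly all of that bias.
- *That sequences could run far past 30 while waiting for six crossovers in successive patients.* The wording permits this, but about 60 evaluable patients per age group cap any separate sequence, so it is an unlikely intention.

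**Conclusion.** This is a gap in specification of minor to moderate weight. It is not an arithmetic error, and it is not evidence that any sequence was run wrongly. The allocation rule and the end point in 5.1.7 and 5.1.8 do not match the sizing in 6.3.4 or the by-age analysis in 6.3.2 and the SAP.

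Followed literally, the missing age condition costs the SAP's CIR modest precision if the groups are alike and more as they diverge. It would shrink age differences only under a crossover mean. The end point matters more for precision: stopping at six crossovers would raise the CIR error by roughly 50% to 80% over the σ range examined. With no age difference and 30 patients per sequence, there is no bias and little loss. All simulated sizes rest on a normal threshold curve, an assumed σ and assumed age differences.

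**What to change.** **Allocation.** In protocol 5.1.7 and 5.1.8 and SAP item 1 (with Fig 1), state: *Six sequences are run, one per stimulus and age group. Each has its own first patient. Each later target is set by the previous patient in the same age group who received that stimulus.* Align the abstract and synopsis.

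**End point.** Replace the crossover wording in 5.1.7 with: *Each sequence ends at the planned 30 responses per stimulus per age group. Six crossovers are a minimum for estimation, not a stop. A sequence that falls short is analyzed as it stands, with its number reported.*

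**Sequences already run.** The SAP dates recruitment February 2023 to June 2024, so for these the change is disclosure: report how each was allocated and when it ended. If any were shared between age groups, say so and base the age-specific SEF50 on the SAP's CIR, not on the crossover mean.

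**Cost.** A few sentences in each document, and one target list per stimulus and age group. No extra patients are needed, because 30 remains the planned number and is not made a floor.
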